13.3 DEVICE SUCCESS ENDPOINT ANALYSIS

The device success endpoint will be summarized by counts and percentages for the ITT and as-treated cohort. The endpoint will be assessed at the 1 month, 6-month, 1 year, 2-year and 3-year follow-up intervals.

In addition to the device success analysis, hemodynamic performance data will be obtained at the following time points: baseline, 1 month, 6 months and annually up to 3

years. Descriptive statistics such as mean, standard deviation will be calculated for the continuous echo variables as well as the change from baseline for each variable.

13.4 PROCEDURE SUCCESS ENDPOINT ANALYSIS

The procedure success endpoint will be summarized by counts and percentages for the as-treated cohort. The endpoint will be assessed at the index procedure hospital discharge.

13.5 CLINICAL SUCCESS ENDPOINT ANALYSIS

The clinical success endpoint will be summarized by counts and percentages for the as-treated cohort. The endpoint will be assessed at the 1 month follow-up interval.

Patient specific functional status (NYHA Class), exercise capacity (6MWT), blood test parameters, and quality of life (SF-12 and KCCQ) metrics will be assessed at baseline, 1 month, 6 months and annually up to 3 years. The distribution (numbers of patients and percentages) in the various NYHA classes will be tabulated at baseline, 1 month, 6 months and annually up to 3 years. Patients that are missing a baseline or follow up values will be excluded from the analysis. Patients that undergo any type of repair or replacement procedure for the tricuspid valve will be excluded from these analyses at the time of the reintervention and summarized in a table.

Rehospitalization rates will be assessed at 1 month, 6 months and annually up to 3 years.

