7.3 EXCLUSION CRITERIA

The Investigator at the study site must exclude patients if any of the exclusion criteria are present. The following are the criteria for exclusion from participating in the clinical study:

1. Echocardiographic/CT parameters (any of the following):
 - a. Vessel access or right heart anatomy precluding proper device introduction, deployment and function
 - b. LVEF $<$ 30%
 - c. Severe right ventricular dysfunction as assessed by the core lab
 - d. Patients with systolic pulmonary artery pressure $>$ 60 mmHg
2. Primary tricuspid disease (e.g. rheumatic, myxomatous degeneration, tricuspid valve prolapse, tricuspid stenosis)
3. Previous tricuspid leaflet repair or tricuspid valve replacement
4. Presence of two or more trans-tricuspid leads or any single trans-tricuspid lead:

- a. Precluding proper placement of or interferes with device
 - b. Implanted within the last 180 days
 - c. With pacemaker dependency
5. Severe aortic, mitral and/or pulmonic valve stenosis and/or regurgitation
 6. Active endocarditis within 90 days of the scheduled implant
 7. Significant pericardial effusion
 8. Intra-cardiac mass, thrombus, or vegetation
 9. Untreated clinically significant coronary artery disease requiring revascularization
 10. Recurrent (>2 per 12 months) hospitalizations or ER visit for COPD exacerbation
 11. MI or known unstable angina within 30 days prior to the index procedure
 12. Any therapeutic invasive cardiac procedure within 30 days prior to the index procedure, or any dual anti-platelet therapy (DAPT) requirement which cannot be interrupted for 7 days
 13. Any cardiac surgery, within 3 months prior to procedure
 14. Hemodynamic instability or on IV inotropes within 30 days of the scheduled implant
 15. Severe uncontrolled hypertension (SBP \geq 180 mmHg and/or DBP \geq 110 mm Hg)
 16. Cerebrovascular Accident (CVA) or TIA within the past 30 days
 17. Kidney dysfunction with estimated Glomerular Filtration Rate (eGFR) < 30 ml/min/1.73 m² or patient is on chronic dialysis
 18. Any physical impairment which limits the patient's capacity to complete functional testing due to other medical conditions independent of their TR (e.g. orthopedic condition)
 19. Significant frailty (i.e. Katz Index of Independence in Activities of Daily Living (ADL) \leq 2) within 90 days of scheduled implant procedure
 20. Continuous home oxygen for primary severe COPD
 21. Chronic anemia (Hgb < 9 g/dL) not corrected by transfusion

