13 STATISTICAL ANALYSIS

13.1 SAMPLE SIZE

This clinical study will enroll 60 patients. This sample size was established based on typical sample sizes for early feasibility studies and no statistical justification was utilized.

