**3.3.3 FDA Individual Patient Success (at 6-months & 1 year): Effectiveness**

- Device Success and all of the following:
  - a) No re-hospitalizations or re-interventions for the underlying condition (e.g. HF or TR)
  - b) Improvement vs. baseline in symptoms (e.g. NYHA Class improves from baseline)
  - c) Improvement vs. baseline in functional status (e.g. 6MWT improves from baseline)
  - d) Improvement vs. baseline in QoL (e.g. SF-12, KCCQ improves from baseline)

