## 6. DATA AND ANALYSIS CONVENTIONS

### 6.1 General Conventions

- For continuous variables, summary statistics will include number of observations, mean, median, standard deviation, minimum, maximum, and 95% confidence intervals (based on normal distribution) per table shells. Nonparametric techniques may be used if the data does not meet the assumptions of parametric tests.
- For ordinal data, the count and percentage of patients will be presented.
- For categorical and qualitative variables, summary statistics will include number of observations, percentage, and 95% Clopper-Pearson confidence intervals per table shells. In general, the denominator for the percentage calculation will be based on total number of patients with evaluable data for a specified time point unless otherwise specified. Patients with missing data will be excluded from the denominator.
- Survival analysis techniques will be used to analyze the time-to-event variables. Summaries will include the number of patients at risk, number of events, number of patients with the event, and Kaplan-Meier estimates at given time points. Patients without events will be censored at their last known event-free time point. If this event-free time point occurs after the analysis time point, the days to event variable will be set equal to the analysis time point so that the patient will be included in the analysis. For patients who did not have an event or early withdrawal and have not yet completed the analysis visit, they will be censored at their last participation date. Standard errors will be calculated using Greenwood's formula and SAS defaults will be used for confidence bands and transformations on  $S(t)$  for the confidence limits. Kaplan-Meier event rate plots will be presented via the cumulative hazard rate plotted against the days from implantation.

- [REDACTED]

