### 6.2 Handling of Missing Data

All statistical analysis on the endpoints will be performed using only those patients with available data required for endpoint analysis. No missing value imputation will be performed.

 Edwards	Revision Date: April 1, 2019		Rev	3.0	For Use Only by Affiliates of Edwards Lifesciences	Page 15 of 18
	Title	Statistical Analysis Plan for FORMA EFS				

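### Every patient without a follow-up six-minute walk is excluded whatever the reason, so descriptive 6MWT change may be overstated if some attending patients are too ill to walk

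*Protocol*

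**What the plan says.** Protocol 13.5 makes the walk a repeated outcome: "exercise capacity (6MWT), blood test parameters, and quality of life (SF-12 and KCCQ) metrics will be assessed at baseline, 1 month, 6 months", and then annually to 3 years. The same paragraph sets the rule for incomplete data: "Patients that are missing a baseline or follow up values will be excluded from the analysis". It also removes patients from these summaries from the time of a tricuspid reintervention.

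The SAP agrees. Section 6.2 states "All statistical analysis on the endpoints will be performed using only those patients with available data required for endpoint analysis" and "No missing value imputation will be performed". Section 6.1 adds, for percentages, "Patients with missing data will be excluded from the denominator", unless otherwise specified. Section 8.4.2 lists exercise capacity without any rule for a walk that could not be performed.

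The walk also enters a composite. SAP 3.3.3 defines FDA Individual Patient Success at 6 months and 1 year as device success plus four further conditions. Condition (c) is "Improvement vs. baseline in functional status (e.g. 6MWT improves from baseline"). SAP 8.3 reports the composite and each component separately.

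Exclusion 18 in Protocol 7.3 keeps out patients with a physical impairment limiting their "capacity to complete functional testing due to other medical conditions independent of their TR". Neither document mentions a walk not done because of illness.

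**The concern.** Leaving out missing walks does little harm when they are missing for reasons unrelated to the patient's condition. It is not harmless when the reason is the outcome itself. These patients enter with symptomatic severe tricuspid regurgitation and are followed for 3 years. A patient who attends a visit but cannot walk because of cardiac or general decline has a poor functional outcome, yet the plan's rules record that outcome as no data.

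The paired change then describes those still fit to walk. The percentage improved in component (c) loses from its denominator patients who had not improved. There is no control arm in which similar selection would show.

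One stated objective is to guide the design of future studies, and an optimistic 6MWT change could be carried into their planning. The 30-day MAE composite and device, procedural and clinical success do not use the walk and are untouched.

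**Working it through.** The plan has no figure to reproduce. It gives no expected 6MWT change, SD or rate of missing walks, and of the 60 patients it says: "This sample size was established based on typical sample sizes for early feasibility studies and no statistical justification was utilized". Every input below is an assumption, chosen to show direction and range.

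**Assumed inputs.** *p* is the share of patients unable to walk through illness. Walkers' change is normal with mean 20 m and SD 60 to 80 m. The improvement rate among walkers is 60%. The observed-pairs analysis reports +20 m and 60% whatever *p* is.

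**1. Median change, unable patients ranked lowest.** The overall median is the walkers' quantile at q = (0.5 − p)/(1 − p), so median = 20 + SD × z(q).

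| p | q | z(q) | Median, SD 60 | Median, SD 80 |
|---|---|---|---|---|
| 5% | 0.45/0.95 = 0.474 | −0.066 | +16.0 m | +14.7 m |
| 10% | 0.40/0.90 = 0.444 | −0.140 | +11.6 m | +8.8 m |
| 15% | 0.35/0.85 = 0.412 | −0.223 | +6.6 m | +2.2 m |

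**2. Percent improved, unable counted as not improved.** The rate is 0.60 × (1 − p), which gives 57%, 54% and 51% for p = 5%, 10% and 15%.

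**3. Mean change under two opposite conventions.**
- Unable patients assumed unchanged: 20 × (1 − p) = 19, 18 and 16 m at 5%, 10% and 20%. The overstatement is 1 to 4 m.
- Unable patients scored 0 m, with an assumed mean baseline *b* of 150 to 250 m: (1 − p) × 20 − p × b = +11.5 to +6.5 m at 5%, +3.0 to −7.0 m at 10%, and −14.0 to −34.0 m at 20%.

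**4. Selection alone, with no score assigned to anyone.** A simulation assumed no true mean change, baseline mean 250 m with SD 100 m, and SD of change 60 to 80 m. The lowest follow-up distances were dropped. The apparent gain was 3.4 to 5.6 m when 5% were dropped, 6.1 to 9.9 m at 10%, and 10.9 to 17.5 m at 20%.

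On every convention tried the direction is the same: the observed-pairs summary is too favourable. The size depends on *p*, which is unknown, and on how an unable patient is valued, which the plan does not settle.

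**The case against.** The strongest reply is that the documents never describe such walks, so overstatement is conditional on patients who may be few or absent. That stands. Several stronger readings should also be resisted.

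- **That exclusion 18 shows later inability to be due to the valve disease.** It applies only at entry. Over 3 years, new orthopaedic, neurological or other limits can arise. The criterion makes decline a plausible reason, no more.
- **That a modest share unable to walk erases the gain.** With 0 m scoring and a 200 m baseline, the mean gain does vanish at 20/220 = 9.1% unable. But 0 m is a scoring convention, not the true change, and the median in the table above stays positive through 15%.
- **That a patient too ill to walk always leaves the composite.** SAP 3.3.3 requires every condition to be met. Such a patient may already fail on NYHA class, quality of life or rehospitalization, and the SAP does not say that one missing component makes a known failure not evaluable. SAP 6.2 can be read that way, but it need not be. The walk is also only given as an example there. Only the separately reported component is clearly exposed.
- **That the case report form lacks a reason field.** Protocol Table 10 lists pre- and post-walk data and results in a list stated not to be exhaustive. The form and table shells are not available, and one SAP 6.1 convention is redacted. Missed visits must also be documented (Protocol 8.8) and count as deviations (14.3).

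The SAP also reports numbers of observations, disposition by visit, NYHA class, quality of life, rehospitalization and adverse events. These make a shrinking sample visible, but they neither show why walks are missing nor correct the 6MWT summary.

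**Conclusion.** The point holds as a conditional one. As written, the plan excludes a walk not done through illness in the same way as any other missing walk. If such patients occur, the descriptive 6MWT change and component (c) are biased upward. The 6MWT is not a feasibility endpoint and no efficacy test rests on it, so the study's main conclusions do not depend on this.

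The size cannot be derived from the documents. The assumed cases run from an overstatement of 1 to 4 m in the mean (unable patients unchanged, 5% to 20% unable) to a median lower by about 13 to 18 m at 15% unable (worst rank). The documents do not support saying that improvement is in fact overstated, or by how much. They do support settling the rule before the results are read.

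**What to change.** 1. Record why each 6MWT was not done, if the eCRF does not already do so.
2. At each visit, tabulate patients as walked, unable through illness, died, or missing for other reasons, with unknown reasons on a separate line.
3. In SAP 3.3.3(c), count inability through illness as not improved. State that a patient who fails any known component of the composite is a failure even if another component is missing.
4. Keep the observed-pairs analysis. Beside it, pre-specify a sensitivity analysis of median change and percent improved, with illness-related inability ranked worst and walks missing for unrelated reasons left missing.

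The cost is at most one eCRF field, one table and a few SAP sentences. The reported gain may be smaller. For past visits, including those of the first 30 patients, who enrolled before Rev L, reasons may be incomplete and would have to be judged without blinding. That is why unknown reasons should be shown separately and not assigned to either group.

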13.7 MISSING DATA

All possible steps will be taken to minimize missing data in the study, including monitoring of data forms for completeness by the sponsor and efforts to track and maintain contact with study patients during the follow-up period by the investigational sites.

Unless otherwise specified, all statistical analyses for the endpoints will be performed using available data. No missing value imputation will be performed.

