### 2.3 Sample Size Consideration

This clinical study will enroll 60 patients. This sample size was established based on typical sample size for early feasibility studies and no statistical justification was utilized.

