#### 8.4.2 Clinical parameters

Re-hospitalization rates will be assessed at 1 month, 6 months and annually up to 3 years.

Time to first Heart Failure Re-hospitalization will be assessed via the Kaplan-Meier method for the AT cohort. In addition, the HF Re-hospitalization rate (number of HF Re-hospitalization per patient-year) will be analyzed.

Patient specific functional status (NYHA Class), exercise capacity (6MWD), and quality of life (SF-12 and KCCQ) metrics will be assessed at baseline, 1 month, 6 months, and 1 year and beyond.

Patients that undergo any type of repair or replacement procedure for the tricuspid valve will be excluded from analysis at the time of the reintervention. Only data up to the point of reintervention will be used.

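### NYHA, 6MWT and quality-of-life tables to 3 years cover only survivors with data, and the plan has no separate handling of death, a gap that matters most at years 2 and 3

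*Protocol*

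**What the plan says.** Protocol 13.5 follows NYHA class, 6MWT, SF-12 and KCCQ to 3 years. For NYHA it states: "The distribution (numbers of patients and percentages) in the various NYHA classes will be tabulated at baseline, 1 month, 6 months and annually" (continuing to year 3). The rule for an absent value is: "Patients that are missing a baseline or follow up values will be excluded from the analysis". Protocol 13.7 adds: "No missing value imputation will be performed".

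The SAP keeps the same approach. Section 6.1 takes patients evaluable at the given time point as the denominator and says: "Patients with missing data will be excluded from the denominator". Section 6.2 says: "All statistical analysis on the endpoints will be performed using only those patients with available data required for endpoint analysis". Section 8.4.2 says the functional and quality-of-life "metrics will be assessed at baseline, 1 month, 6 months, and 1 year and beyond". It has no rule for patients who die.

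Two other groups also leave these tables. Protocol 13.5 and SAP 8.4.2 stop using a patient's data at tricuspid reintervention. Protocol 8.10 exits explanted patients after a limited safety follow-up.

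Death does count elsewhere. FDA Device Success (SAP 3.3.1) requires the patient to be alive, at 1 month and every later visit. FDA Individual Patient Success (SAP 3.3.3) adds improvement in NYHA, 6MWT and quality of life, at 6 months and 1 year only.

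**The concern.** A patient who died before a visit has no NYHA class, walk distance or questionnaire score at that visit. Under the stated rules that patient leaves both numerator and denominator, exactly like one who missed the appointment. The composite success endpoints have a component that a dead patient fails; these tables have none, so nothing keeps the patient in.

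Deaths before year 3 are to be expected. Protocol 1.1.2 describes severe TR as having a poor outlook, and exclusion 34 removes only patients expected to live less than 12 months, while follow-up is 3 years. There is no control arm in which similar attrition would show. One objective of the study is to guide the design of later studies. A year-3 NYHA table taken as the state of the treated cohort could mislead that planning.

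**Working it through.** **Inputs.** The documents give N = 60 enrolled, of which Protocol 13.1 says: "This sample size was established based on typical sample sizes for early feasibility studies and no statistical justification was utilized". The as-treated set can be no larger. No mortality, dropout, baseline NYHA or 6MWT figure is given, and the plan has no figure of its own to reproduce. Everything below on mortality *m*, status and class mix is assumed and shown as a range. Death is taken as the only loss.

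**Step 1: status among survivors against status in the cohort.** Let *p* be the share of survivors in NYHA I/II. The planned table reports *p* whatever the mortality. The share of the treated cohort alive and in I/II is *p*(1 − *m*), so the gap is *pm*. With *p* = 0.75:

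| Cumulative mortality | Table shows | Alive and I/II | Gap (points) |
|---|---|---|---|
| 10% | 75% | 0.75 × 0.90 = 67.5% | 7.5 |
| 20% | 75% | 0.75 × 0.80 = 60.0% | 15.0 |
| 30% | 75% | 0.75 × 0.70 = 52.5% | 22.5 |
| 40% | 75% | 0.75 × 0.60 = 45.0% | 30.0 |

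**Step 2: the same for within-patient improvement.** Suppose half of the survivors improve and 6, 12, 18 or 24 of 60 die. Available-case reporting gives 27/54, 24/48, 21/42 and 18/36, each 50.0%. Over all 60 the shares alive and improved are 27/60 = 45.0%, 24/60 = 40.0%, 21/60 = 35.0% and 18/60 = 30.0%. This result needs no assumption about who dies, and pairing does not change it.

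**Step 3: drift, if the baseline column is not matched.** Assume 15 of 60 (25.0%) are in I/II at baseline and no patient ever changes class. Deaths are rounded to whole patients. The later I/II share is (15 − deaths from I/II)/(60 − all deaths):

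| Deaths | All deaths from III/IV | About 90% from III/IV | About 75% (baseline mix) |
|---|---|---|---|
| 6 | 15/54 = 27.8% | 14/54 = 25.9% | 13/54 = 24.1% |
| 12 | 15/48 = 31.2% | 14/48 = 29.2% | 12/48 = 25.0% |
| 18 | 15/42 = 35.7% | 13/42 = 31.0% | 11/42 = 26.2% |
| 24 | 15/36 = 41.7% | 13/36 = 36.1% | 9/36 = 25.0% |

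For 6MWT with no patient changing, the apparent mean gain is (deaths/60) × *k*, where *k* is how far those who die were below survivors at baseline. For *k* = 50 m it is +5 m (6 deaths) to +20 m (24 deaths). For *k* = 100 m it is +10 to +40 m. For *k* = 0 it is nil.

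**Step 4: the same cases with a matched baseline.** Each later share or mean is compared with the baseline of the same patients, so every change in Step 3 becomes 0. Steps 1 and 2 stand.

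**Step 5: which reading does the plan intend?** Protocol 13.5 requires both a baseline and a follow-up value, which points to matching. SAP 6.1 sets the denominator time point by time point, which points away from it. SAP 8.4.1 calls the echocardiographic comparison paired; SAP 8.4.2 does not use the word for NYHA, 6MWT or quality of life. The question is open for the NYHA distribution. A mean change within patients is matched by construction.

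**The case against.** The strongest reply is that the exclusion sentence is a matched-pair rule. SAP 8.4.1 uses nearly the same sentence and calls the analysis paired. A reader might infer that the cohort will seem to improve as its sickest members die. The documents do not support that as a flat statement. It needs an unmatched baseline and selective mortality, and the documents settle neither. When deaths follow the baseline mix, Step 3 shows essentially no drift.

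Second, the plan does not ignore death. FDA Individual Patient Success is close to an alive-and-improved measure at 6 months and 1 year. FDA Device Success reports survival to year 3, and SAP 7.1 tabulates disposition at each interval. This narrows the gap but does not close it. No measure joins survival with function at years 2 and 3, and a separate disposition table leaves the functional percentages unchanged.

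Third, a reader might take these tables to be the main evidence of benefit after 30 days. Protocol section 5 does not list NYHA, 6MWT or quality of life as endpoints in their own right. The plan also has echocardiography to 3 years, rehospitalization rates, a Kaplan-Meier analysis of heart-failure rehospitalization and the FDA endpoints. These tables are descriptive, in a study with no formal sample-size basis.

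Fourth, SAP 6.1 defers layout to table shells that are not in the documents. The shells might show deaths beside NYHA, but the written denominator rule would still exclude them.

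**Conclusion.** The point holds as a limit on what the tables describe. As written, the NYHA, 6MWT, SF-12 and KCCQ summaries describe survivors with data and overstate status if read as the treated cohort's. The gap is most important at years 2 and 3. Favourable drift is a second, conditional problem: possible if the baseline is unmatched and sicker patients die, absent if it is matched.

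The 7.5 to 30 points in Step 1 is the distance between two quantities, status among survivors and status in the whole cohort, under an assumed 75% and an assumed mortality of 10% to 40%. It should not be quoted as an estimated bias for this trial. The safety and performance endpoints of Protocol section 5 are unaffected.

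**What to change.** Amend SAP 8.4.2 and the related table shells:

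- At each visit, base NYHA percentages on all as-treated patients who have reached that visit time. Beside the four classes, add rows for dead; tricuspid reintervention or explant; alive but not assessed; and withdrawn or lost with vital status unknown. State an order of precedence so that each patient falls in one row.
- Report the proportion alive and improved on 6MWT and KCCQ over the same denominator, at least at years 2 and 3.
- Keep the paired change, label it as survivors with data, and show the baseline of those same patients separately for each visit. This also settles whether the comparison is matched.

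The unknown-status row is needed because Protocol 8.9 ends study follow-up procedures at withdrawal or loss, so a clean split into dead and alive will not always be possible. The reintervention or explant row is needed because those patients leave the tables or the study under the plan's own rules.

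The cost is wording and a little more table work, with no new visits or assessments. The reported percentages will look less favourable.
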